A key to cost-effective management of DM is an accurate risk assessment and stratification system that identifies high-risk patients for more intensive medical and psychosocial interventions. At the same time, an accurate estimation of risk distribution can inform policy-makers to allocate appropriate resources and plan services that can maximum population health benefit for DM patients. Existing prediction functions commonly used include the Framingham [10-year] (9, 10), the United Kingdom Prospective Diabetes Study (UKPDS) [5-year] (11, 12) and the local (Joint Asia Diabetes Evaluation (JADE) [5-year] (13, 14) models. However, our earlier study on 10,969 diabetic patients managed in the HA primary care clinics showed none of these models was accurate in predicting the observed events over a 4-year follow up for this patient population (15). The Framingham models overestimated the risks of CHD and stroke by 2.0 times and 23%, respectively(15). Several other studies have also concluded that the Framingham models were not applicable to Chinese populations (16). The UKPDS risk prediction models also showed a tendency to overestimate the risk of CHD and stroke by 5.1 times and 51%, respectively (15). The JADE prediction models, although developed from the local Chinese population, overestimated the 4-year CHD, stroke rates by 2.9 times and 41%, respectively, when compared to the actual 4-year observed incidences (15). The JADE prediction models were developed from data of Chinese diabetic patients under specialist care who are more likely have more severe disease and many had complications such as stroke or CHD at baseline (13, 14), which may explain why they tend to over predict complications in primary care DM patients. The

cohort from JADE was collected almost 20 years ago (1995) and the number of subjects (around 7000) was relatively small, which may not be generalizable to the 400,000 DM patients under HA care. Furthermore, JADE only provides 5-year risk prediction although 10-year risk is the international standard (17).

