1. Calculate the 10 years incidence of total CVD, all-cause mortality and each major DM complication in Chinese DM patients in primary care.
2. Determine the risk factors that significantly predict total CVD, all-cause mortality and each major DM complication for Chinese DM patients in primary care.
3. Develop and validate risk prediction models for total CVD, all-cause mortality and each major DM complication for Chinese DM patients in primary care.
4. Develop a risk prediction nomogram and chart for the risk of total CVD, all-cause mortality for Chinese DM patients in primary care

Hypotheses

The following hypotheses will be tested:

1. Patient socio-demographic, clinical parameters, disease characteristics, and treatment modalities (these independent variables are described in the Methods section) are predictive of 10-year risk of total CVD, all-cause mortality and individual DM complication as a dependent variable.
2. The risk prediction models for total CVD, all-cause mortality and individual DM complication developed in this study can have over 70% of discriminating power.

d) **Plan of Investigation:**

(i) **Study design**

A 10-year retrospective study on a population-based cohort of Chinese DM patients in primary care.

(ii) **Subjects**

The cohort will include all patients with a documented clinical diagnosis of DM and were receiving care in the Hospital Authority (HA) primary care General Out-Patient Clinics (GOPC) and Family Medicine Clinics (FMC) on or before 1 July 2006 identified from the HA clinical management system (CMS) database.

Inclusion criteria

1. Age \geq 18 years old
2. At least 1 GOPC/FMC attendance on or within 1 year before 1 July 2006
3. Had a CMS record of the coding of ICPC-2 of T89 (Diabetes insulin dependent) or T90 (Diabetes non-insulin dependent) on or before 1 July 2006

Exclusion criteria

1. Patients who had a diagnosis of any DM complications defined by the relevant ICPC-2 or ICD-9-CM (shown in the Method section) on or before 1 July 2006.
2. Patients exclusively managed by Specialist Out-Patient Clinic (SOPC) on or before 1 July 2006.

Sample size calculation

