The detailed sample size calculation for each study outcome is attached in Appendix B. The required sample size is based on the requirements for the development and validation of the least common DM complication of ESRD. Specifically, based on our previous study, the 5-year incidence of ESRD was 1.9%(8), which can be extrapolated to a 10-year incidence of ESRD was 3.8% by assuming a constant incidence rate over time. To develop the risk prediction model for ESRD by multivariable Cox proportional hazard regressions with forward stepwise variables selection on 16 potential risks factors, we need 21,053 subjects using the 1 in 50 rule that 1 candidate predictor can be studied for every 50 events (23). To validate the risk prediction models, the area under the receiver operating characteristic curve (AUC) will be used to assess the discriminatory power of the predictive model on a separate sample of subjects. With 10 years incidence rate of ESRD was 3.8%(8), a total 14,307 subjects (544 subjects with ESRD and 13,763 subjects without ESRD) is needed to

ensure a precision of 0.05 for AUC of 0.7 by a 95% confidence interval.

Hence, a total 35,360 male and 35,360 female are needed for the development (training dataset) and validation of risk prediction models stratified by gender. The HA data set that we have obtained for our 5-year evaluation of quality of care and effectiveness of RAMP-DM study(8) has identified 120,857 DM patients under the care of public primary care on or before 1 Jan 2009, so we should be able to obtain sufficient number of subjects.

(iii) **Methods**

Each patient will be followed from 1 July 2006 to 31 December 2016 for the development of the indicator DM complications and mortality.

Definition of indicator DM complications

The incidence of four major DM complications (CHD, stroke, heart failure and ESRD), total CVD and all-cause mortality will be calculated. The incidence is counted from the earliest date of documented diagnosis defined by the relevant ICPC-2 and/ or ICD-9-CM coding recorded in the HA CMS database from 1 July 2006 to 31 December 2016. The relevant ICPC-2 and ICD-9-CM codes of each DM complication and mortality are determined by the academic and HA clinician co-investigators as listed below:-

1. CHD (ischaemic heart disease, myocardial infarction (MI), coronary death or sudden death) is defined by any of ICPC-2 K74 to K76 and ICD-9-CM 410.x, 411.x to 414.x, 798.x

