To validate the risk prediction models for total CVD, all-cause mortality and each of 4 major DM complications, they will be applied to the data of the one third validation sample to estimate the risk level of the subjects. A receiver operating characteristic (ROC) curve of predicted risk against observed events will be used to calculate the area under the curve (AUC) for assessing overall prediction accuracy. The corresponding 95% confidence interval will be obtained by bootstrapping of size 2000. An AUC of less than 0.7 indicates limited discriminating power, 0.7 to 0.8 is acceptable, and higher than 0.8 suggests strong discrimination of the predictive models. Using the optimal prediction risk threshold identified by ROC curve in training dataset, and the corresponding sensitivity and specificity of the models against observed events will be calculated to further evaluate the performance of the models.

Calibration will be used to measure how closely predicted outcomes agree with actual outcomes. Calibration of the model's ability to correctly estimate the absolute risks will be examined by modified Hosmer-Lemeshow test and calibration plots. The modified Hosmer-Lemeshow test for time to event data measures how well the predicted probability of the expected event rate agrees with the observed event rate, where a *p*-value higher than 0.05 indicates good model calibration. In a calibration plot of the observed incidence of events against the predicted risk shows the scatter along the 45° line of perfect fit between predicted risk and observed incidence of event throughout the entire risk spectrum.

The D statistic, R^2 statistic and Brier score will be calculated for assessing the predictive power of the model. The D statistic is a measure of discrimination where higher value indicates better discrimination. The R^2 statistic is a measure of explained variation with a higher value indicating better performance. The Brier score is a measure of goodness of fit in which a lower value mean higher accuracy.

Development of a risk prediction nomogram and chart

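### Every validation measure is absolute and computed for the new equations alone, so the plan as written cannot show, in the same patients, a gain over age or over the existing risk scores

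*Combined protocol and SAP*

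**What the plan says.** Hypothesis 2 (section c) is the only hypothesis on model performance. It covers total CVD, all-cause mortality and the individual complications, and expects that the models "developed in this study can have over 70% of discriminating power". The section on validation of the models sets the bands: "An AUC of less than 0.7 indicates limited discriminating power, 0.7 to 0.8 is acceptable, and higher than 0.8 suggests strong discrimination". The sample size section plans validation around one AUC: 14,307 subjects per sex, 544 of them with ESRD, are meant to "ensure a precision of 0.05 for AUC of 0.7 by a 95% confidence interval".

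The validation section applies the new equations to the held-out third. It plans AUC with a bootstrap interval (2000 resamples), sensitivity and specificity at the training threshold, a modified Hosmer-Lemeshow test with its own criterion (p above 0.05), calibration plots, the D statistic, R² and the Brier score. None is planned for any other model.

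The Introduction makes a comparative case. It cites an earlier study of 10,969 HA primary care patients that "showed none of these models was accurate in predicting the observed events over a 4-year follow up for this patient population", and describes over-prediction of CHD and stroke by Framingham, UKPDS and JADE. It then lists features that new models should consider: sex-specific modelling, age interactions, quadratic terms, repeated measurements and drug treatment.

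**The concern.** The rationale is comparative and the yardsticks are absolute. Two gaps follow.

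First, the cohort takes every adult from 18 with no upper age limit, and age is itself a candidate predictor. The AUC of any model in such a cohort depends heavily on the spread of age. A model that owed nearly all its discrimination to age could be reported as acceptable, and the reader could not tell how much the laboratory, clinical and treatment variables contributed.

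Second, the fault reported in the existing scores is over-prediction. AUC depends only on how patients are ranked, so rescaling a score's baseline leaves its AUC unchanged. An AUC threshold therefore says nothing about that fault. The Introduction gives no AUC for the existing scores, so it is not known from the documents whether they rank patients worse than the new equations will. A rescaled existing score is the simpler alternative, and the plan does not test it.

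At stake is whether the report can say that the new equations predict better than something simpler, which matters for equations meant to guide risk stratification in HA programmes.

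**Working it through.** **1. The plan's own sizes.** The development size uses 3.8% ten-year ESRD incidence ("10-year incidence of ESRD was 3.8% by assuming a constant incidence rate over time"), 16 candidate predictors and 50 events per predictor: 16 × 50 / 0.038 = 21,052.6, rounded up to the stated 21,053.

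For validation, the Hanley–McNeil variance with A = 0.70, n₁ = 544 and n₀ = 13,763 is

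var = [A(1−A) + (n₁−1)(Q₁−A²) + (n₀−1)(Q₂−A²)] / (n₁n₀), with Q₁ = A/(2−A) = 0.5385 and Q₂ = 2A²/(1+A) = 0.5765.

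This gives SE = 0.01275, half-width 1.96 × 0.01275 = 0.025 and full width 0.050. The stated precision is thus the full width of the interval around one AUC. The sum 21,053 + 14,307 = 35,360 per sex also agrees. The sizes reproduce, and they were set to estimate a single AUC, not a difference. Appendix B, which holds the detailed calculation, is not in the available text.

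**2. AUC of age alone.** Every input here is an assumption, because the documents give none of them: age normal with mean 62, truncated to 18–100; SD 10–13 years, with 8 as a narrow case; ten-year incidence m of 10% or 25%; constant log hazard ratio g per year of age. The ten-year risk at age x is p(x) = 1 − exp{−exp[c + g(x − 62)]}, with c solved so that the mean risk equals m. The AUC is the probability that a random case is older than a random non-case, by numerical integration. Each cell gives the result at m = 10% / 25%.

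| HR per year | SD 8 | SD 10 | SD 11 | SD 12 | SD 13 |
|---|---|---|---|---|---|
| 1.05 | 0.614 / 0.624 | 0.641 / 0.652 | 0.654 / 0.666 | 0.666 / 0.679 | 0.678 / 0.691 |
| 1.06 | 0.635 / 0.646 | 0.667 / 0.679 | 0.681 / 0.694 | 0.696 / 0.709 | 0.709 / 0.722 |
| 1.08 | 0.675 / 0.688 | 0.714 / 0.727 | 0.732 / 0.745 | 0.748 / 0.761 | 0.763 / 0.776 |
| 1.10 | 0.712 / 0.725 | 0.756 / 0.768 | 0.775 / 0.786 | 0.792 / 0.803 | 0.808 / 0.818 |
| HR at which AUC = 0.70 | 1.093 / 1.086 | 1.074 / 1.068 | 1.067 / 1.062 | 1.062 / 1.057 | 1.057 / 1.053 |

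If the mortality gradient is 1.08–1.10 per year and the SD 10–13, age alone gives 0.71–0.82. If the CVD gradient is 1.05–1.06, it gives 0.64–0.72, and 13 of those 16 cells fall below 0.70. At SD 8 age passes only above 1.086–1.093 per year.

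**3. Whether a paired comparison is feasible.** Assume AUC 0.75 for the full model and 0.70 for the reference, correlation r between the two AUCs of 0.5–0.9, 80% power and two-sided 5%. The detectable difference is 2.80 × √(s₁² + s₂² − 2r·s₁s₂).

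- ESRD, 544 events: s₁ = 0.01227, s₂ = 0.01275, detectable difference 0.016–0.035.
- Mortality, assuming 20% deaths in one third of 35,360 (11,787 per sex, 2,357 deaths): s₁ = 0.00617, s₂ = 0.00647, detectable difference 0.008–0.018.

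The data can support the comparison. In the mortality models even a very small gain would be statistically significant.

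**The case against.** The strongest reply is that the plan does more than test an AUC and never promises superiority. Calibration has its own criterion and is checked in the held-out third, which bears directly on over-prediction. No objective or hypothesis claims improvement over age or an existing score. The Introduction also gives other reasons for new models: UKPDS and JADE are listed as 5-year functions, JADE came from specialist-care patients recruited about 1995, and 10-year models are wanted for primary care. The existing scores were already tested in 10,969 similar patients.

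Much of this stands, and it rules out several stronger readings that a reader might infer.

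- That AUC over 0.70 is the sole measure of success. It is not, given the calibration, D, R² and Brier analyses.
- That the study cannot learn anything about added predictors. Forward stepwise Cox regression tests each variable given those already entered, and quadratic and age-interaction terms are examined. That is evidence of association, though not of the size of any gain in prediction.
- That age alone would meet the threshold generally. The documents hold no figure to support this, the assumed CVD range mostly misses 0.70, and ESRD, CHD, stroke and heart failure were not examined separately.
- That the missing comparison invalidates a planned estimate. It does not.

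What the reply does not answer is that every planned measure describes the new equations alone. Good calibration here, set against an earlier 4-year study, is indirect evidence and not a comparison in the same patients.

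**Conclusion.** The point holds as a limit on what the plan can conclude, and a cheap improvement would lift it. That no reference model is planned can be read from the text and needs no assumption. The likelihood that age alone passes 0.70 is conditional: on the assumptions above it is plausible for mortality and usually not the case for CVD, with break-even at about 1.053–1.074 per year for SD 10–13. The limit lies in the planned analysis and not in the data, since the validation sample could support paired comparisons.

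**What to change.** For each sex and outcome, fit an age-only Cox model in the training two-thirds and apply it to the validation third. Report the AUC difference from the full model with its interval, using the planned 2000 bootstrap resamples, and the Brier difference. Interpret Hypothesis 2 alongside the size of that gain. A rule that the interval merely excludes zero would pass trivial gains in a sample this large.

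As a secondary analysis for CHD and stroke, apply those of the Framingham, UKPDS and JADE equations whose predictors are all in the extract. Use each equation's own horizon, both as published and with the baseline rescaled to this cohort, and report AUC and observed/expected ratios side by side with the new models. Equations with absent predictors are better left out, because fixing those predictors at one value would handicap the published score.

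The age-only comparison uses data already in the extract. The cost is a little more analysis, and a headline result that may look less favourable.

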2. Stoke (fatal and non-fatal stroke) is defined by any of ICPC-2 K89 to K91 or ICD-9-CM 430.x to 438.x.
3. Heart failure is defined by any of ICPC-2 K77 or ICD-9-CM 428.x
4. CVD is defined as the presence of any of CHD, heart failure and stroke ICPC-2 or ICD-9-CM codes listed in 1, 2 and 3 above.
5. ESRD is defined by any of ICD-9-CM 250.3x, 585.x, 586.x, or an eGFR<15mL/min/1.73m².
6. Mortality is identified from the Hong Kong Death Registry.

Risk factors to be Included in the Risk Prediction Models

Risk factors (independent variables) previously found to be associated with DM

complications from the literature (4) and those that are routinely available in primary care are selected to strike a balance between comprehensiveness and feasibility. The potential risk factors that will be explored include those related to patient's socio-demographics, clinical parameters, disease characteristics and treatment modalities. Patient socio-demographics include sex, age and smoking status. Clinical parameters include body mass index (BMI), haemoglobin A1c (HbA1c), systolic and diastolic blood pressure, lipid profile (total cholesterol, HDL-C, LDL-C, triglyceride), estimated glomerular filtration rate (eGFR) and albuminuria. Disease characteristics include the duration of DM and co-morbidity. Treatment modalities include the use of specific anti-hypertensive drugs, insulin, specific oral anti-diabetic drugs and lipid-lowering agents. The operational definitions of the risk factors are shown in appendix A. These factors, except sex, age, duration of DM and co-morbidity, are modifiable, which have implications for practice.

Data collection

In the middle of 2017, anonymous data from 1 January 2006 to 31 December 2016 of all DM patients who satisfy the inclusion criteria and without any exclusion criteria will be extracted by the HA statistics team from the HA clinical management system (CMS) database. We have successful experience in working with the HA in the extraction of similar data from 2009 to 2013 for our extended evaluation on quality of care and effectiveness of RAMP-DM study (7), and we have obtained preliminary agreement from the HA for the data extraction in the present study.

Outcome Measures

1. The incidence of total CVD, all-cause mortality and each of 4 major DM complications over 10 years
2. Factors predictive of total CVD, all-cause mortality and each of 4 major DM complications over 10 years

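### The exclusion rule and the event-dating rule name diagnosis codes only, but ESRD can also be reached by eGFR<15; the plan should apply one ESRD definition in both places (minor)

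*Combined protocol and SAP*

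**What the plan says.** Three statements in section d) of the combined protocol and SAP have to work together.

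- **Exclusion criteria, item 1**, with a cut-off of 1 July 2006, removes "Patients who had a diagnosis of any DM complications defined by the relevant ICPC-2 or ICD-9-CM (shown in the Method section"). It has no laboratory criterion.
- **Definition of indicator DM complications**, opening paragraph: "The incidence is counted from the earliest date of documented diagnosis defined by the relevant ICPC-2 and/ or ICD-9-CM coding". The list that follows is introduced with "The relevant ICPC-2 and ICD-9-CM codes of each DM complication and mortality are determined by" the clinician co-investigators.
- **The same list, item 5** defines ESRD by ICD-9-CM codes or a laboratory value: "585.x, 586.x, or an eGFR<15mL/min" (per 1.73 m²). ESRD is the only one of the four complications with a laboratory route. Item 6 is not a code either: "Mortality is identified from the Hong Kong Death Registry".

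Two further statements bear on the consequences. The candidate predictors include "estimated glomerular filtration rate (eGFR) and albuminuria". Under Data collection, the extract is to hold "anonymous data from 1 January 2006 to 31 December 2016 of all DM patients"; for those meeting the eligibility criteria, these data "will be extracted by the HA statistics team from the HA clinical management system (CMS) database".

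**The concern.** A cohort study of incident ESRD needs the same definition for who is free of disease at baseline and who later becomes a case. Here the outcome is wider than the exclusion, and the dating sentence matches the exclusion rather than the outcome. Two problems follow.

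1. **Prevalent cases can enter.** A patient with an uncoded eGFR below 15 on or before 1 July 2006 already meets the outcome but passes criterion 1. That patient can then be counted as incident. Because eGFR is also a candidate predictor, a recorded low baseline value and the outcome would be the same condition. That would flatter the eGFR coefficient and the ESRD AUC, which the plan judges against 0.7.
2. **eGFR-only events have no date.** A Cox model needs an event time. If the dating sentence is followed literally, events that item 5 includes drop out or are dated late by a subsequent code. This gap depends on no assumption about prevalence.

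**Working it through.** **The passages side by side**

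| Step | Codes | eGFR<15 |
|---|---|---|
| Exclusion at baseline (criterion 1) | yes | not mentioned |
| Outcome (item 5) | yes | yes |
| Date of event | yes | not mentioned |

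If item 5 governs the outcome, an uncoded prevalent case is counted at the next low test. If the dating sentence governs, the same patient is counted when a code is first entered, and eGFR-only events are lost. Under both readings the uncoded prevalent case is in the cohort.

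**The plan's own figures reproduce.** Inputs from Sample size calculation: 10-year ESRD incidence 3.8%, 16 candidate predictors, 50 events each, and a validation sample of 544 cases and 13,763 non-cases.

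- Development: 16 × 50 / 0.038 = 21,052.6, rounded up to 21,053.
- Validation, Hanley-McNeil at A = 0.7: A/(2−A) = 0.5385; 2A²/(1+A) = 0.5765; variance = [0.21 + 543 × (0.5385 − 0.49) + 13,762 × (0.5765 − 0.49)] / (544 × 13,763); SE = 0.01275. The 95% half-width is 0.025 and the full width 0.050, so the stated precision of 0.05 is reproduced as the full width.
- Total per sex: 21,053 + 14,307 = 35,360, with 35,360 × 0.038 = 1,344 expected ESRD events.

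**Illustration of prevalent cases.** The documents give no prevalence *p* of uncoded eGFR<15, so it is assumed. Every such patient is assumed to be counted later.

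- False events per sex = 35,360 × *p*.
- Incidence shift if they come on top of 3.8%: *p* × (1 − 0.038). If they are already inside the 3.8%, the shift is 0.038 − (0.038 − *p*)/(1 − *p*), nearly the same.
- Apparent AUC when the true AUC is 0.70, with f = 14,307 × *p* false events all ranked perfectly and the ranking of true cases unchanged: (544 × 0.70 + f)/(544 + f).

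| *p* | False events | Incidence shift (points) | f | Apparent AUC |
|---|---|---|---|---|
| 0.05% | 18 | 0.05 | 7.2 | 0.704 |
| 0.1% | 35 | 0.10 | 14.3 | 0.708 |
| 0.2% | 71 | 0.19 | 28.6 | 0.715 |
| 0.5% | 177 | 0.48 | 71.5 | 0.735 |
| 1% | 354 | 0.96 | 143.1 | 0.762 |

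The 95% half-width for incidence is 1.96 × √(0.038 × 0.962 / 35,360) = 0.199 points. The shift stays inside it up to *p* of about 0.199/0.962 = 0.207%. Over 0.05% to 0.2%, the true AUC that would just appear as 0.70 is (0.70 × (544 + f) − f)/544 = 0.696, 0.692 and 0.684. Only a model between that value and 0.700 would change sides of the threshold.

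**Illustration of lost eGFR-only events.** If 10%, 25% or 50% of the 3.8% were reached by eGFR alone (assumed) and were dropped, the 800 development events would need 800/(0.038 × 0.90) = 23,392, 800/(0.038 × 0.75) = 28,071 or 800/(0.038 × 0.50) = 42,106 subjects per sex. The documents do not say whether the 3.8% includes such events.

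**What the extract can show.** It begins on 1 January 2006, which is 181 days before 1 July 2006. Low values in that window will be in the analysts' hands; older ones will not.

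**The case against.** The strongest reply is that the code wording is shorthand. Criterion 1 points to the Methods list, and that list is introduced as codes although it contains an eGFR threshold and Death Registry mortality. On that view eGFR<15 already applies throughout. This is a reasonable guess at the intent, and if it is right one clarifying sentence closes the point. But no sentence says so, and a separate HA team applies the written criteria. Appendix A is cited for risk-factor definitions and Appendix B for sample size; neither is cited for exclusion or event dating.

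A second reply is that a consistent code-only reading never counts a later low eGFR as an event. That is so, but it then contradicts item 5 and discards events the plan defines as ESRD. The uncoded prevalent patient still enters and is counted once coded.

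Three further objections stand and limit the point:

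- Recorded January to June 2006 values can be used after extraction, so the problem is partly repairable. Only patients whose qualifying results are all older would be missed.
- The prevalences are not sourced. The AUC figures are not strict bounds, because a distorted eGFR coefficient could also change how true cases are ranked.
- A meeting to confirm the extraction schema and operational definitions is already in the timetable, so the plan has a natural place to settle this.

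**Conclusion.** The inconsistency is real on the text, and it is minor. The exclusion and dating sentences are narrower than the ESRD definition, and read literally they either admit prevalent cases as incident or leave eGFR-only events undated. The effect mainly concerns ESRD incidence, the eGFR coefficient and the ESRD AUC.

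The size is not derivable from the documents. At assumed uncoded prevalences of 0.05% to 0.2% the apparent AUC rises by about 0.004 to 0.015, less than the planned 95% half-width of 0.025, and the incidence shift stays within sampling error. It would matter more at 0.5% or 1%, but nothing in the documents points to such values.

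A reader might infer three stronger things that the documents do not support:

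- *That the ESRD model's result is materially biased, or its 0.7 verdict unsafe.* No prevalence is given, and in the lower range only a model already very close to 0.7 would be affected.
- *That nothing can be done after extraction.* Six months of pre-baseline results will be held.
- *That the matter is wholly confined to the ESRD model.* The CVD and mortality outcome definitions do not use eGFR, but criterion 1 defines one cohort for all six models, so changing it changes membership for all of them.

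**What to change.** Use the plan's own ESRD definition in both places.

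1. **Exclusion.** Exclude patients with any recorded eGFR<15 on or before 1 July 2006. Say whether this applies to the whole cohort under criterion 1 or to the ESRD model only. Preferably the HA team searches laboratory records of any earlier date, since criterion 1 already requires this for codes. At minimum, use the January to June 2006 results in the extract and state that the check is partial.
2. **Dating.** State that an eGFR-defined event is dated at the first qualifying result after 1 July 2006.
3. **Reporting.** Give the number of patients removed by the eGFR rule and the number with no pre-baseline eGFR.

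If the present wording is already meant this way, one clarifying sentence is enough.

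**Cost.** Two lines of text, one laboratory query (its charge is not given in the documents) and a slightly smaller cohort. If the rule goes into criterion 1, membership changes slightly for all six models, including total CVD and mortality and their nomograms and charts; limiting it to the ESRD model avoids this. The schema meeting in June to August 2017 is the natural place to settle it. The timetable puts extraction in September to December 2017, but Data collection says the middle of 2017, so it should be settled before whichever date applies.

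### The 10-year ESRD incidence of 3.8% is twice the 5-year figure with no visible allowance for deaths, so at a constant rate the stated subject numbers give fewer 10-year events than planned

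*Combined protocol and SAP*

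**What the plan says.** Under Plan of Investigation, (ii) Subjects, Sample size calculation, the size is set by ESRD because it is the least common complication. The starting point is a 5-year incidence of 1.9% from an earlier study by the team, "which can be extrapolated to a 10-year incidence of ESRD was 3.8% by assuming a constant incidence rate over time".

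Two per-sex sizes follow.

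- Development: "forward stepwise variables selection on 16 potential risks factors, we need 21,053 subjects", on the rule that "1 candidate predictor can be studied for every 50 events".
- Validation: "a total 14,307 subjects (544 subjects with ESRD and 13,763 subjects without ESRD"), to "ensure a precision of 0.05 for AUC of 0.7 by a 95% confidence interval".

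The two sum to 35,360 men and 35,360 women. The section refers to Appendix B for detail; that appendix is not in the text supplied. The visible text makes no allowance for death or other loss before ESRD.

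Elsewhere, the cohort is fixed by status on or before 1 July 2006 and followed to 31 December 2016. All-cause mortality is one of the six outcomes, and (iii) Methods gives its source: "Mortality is identified from the Hong Kong Death Registry".

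**The concern.** Doubling a 5-year proportion needs as much person-time at risk in years 6 to 10 as in years 1 to 5. A constant incidence rate does not give that. The rate acts only on people who are alive and free of ESRD, and in a closed adult diabetic cohort that group shrinks. The stated assumption and the 3.8% therefore do not agree, and the direction of the error is known: 3.8% is too high.

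ESRD is the outcome chosen so that every other model is adequately sized, and both sizes are set at the minimum for their targets. An overstated event yield therefore bears directly on the two properties the section promises: 50 events per candidate predictor and an AUC confidence interval of the stated precision.

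**Working it through.** **Inputs from the documents.** 5-year ESRD incidence 1.9%; 10-year figure 3.8%; 16 candidates at 50 events each; AUC 0.7, precision 0.05, 95% interval; follow-up 1 July 2006 to 31 December 2016 (10.5 years); 2:1 split; pools of 120,857 (sample size section) and 90,000 (Existing Facilities).

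**Assumed inputs.** 10-year all-cause mortality m of 10%, 20%, 30% or 40%, with constant death hazard. The documents do not say whether 1.9% is a crude proportion (already net of deaths) or a Kaplan-Meier figure, so both are shown.

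**1. Reproducing the plan.**

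- Development: 16 x 50 / 0.038 = 800 / 0.038 = 21,052.6, so 21,053.
- Validation: 14,307 x 0.038 = 543.7, so 544. The Hanley-McNeil standard error at AUC 0.7 with 544 and 13,763 subjects is 0.01275. The full 95% width is 2 x 1.96 x 0.01275 = 0.0500 (0.04997 before rounding), so the precision of 0.05 is a full width.
- Total: 21,053 + 14,307 = 35,360.

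Every printed figure reproduces, with no reserve at 3.8%.

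**2. Constant rate, no deaths.** 1 - (1 - 0.019)^2 = 3.764%. Events: 21,053 x 0.03764 = 792 and 14,307 x 0.03764 = 539, about 1% below 800 and 544.

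**3. Constant rate with deaths.** Let d = -ln(1 - m)/10 and p(t) = h/(h + d) x (1 - exp(-(h + d)t)).

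- Crude reading: h is solved so that p(5) = 0.019.
- Kaplan-Meier reading: h = -ln(0.981)/5 = 0.003837.

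Worked case, m = 30%: d = 0.03567. The crude reading gives h = 0.00419 and p(10) = 3.457%; the Kaplan-Meier reading gives p(10) = 3.169%.

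| 10-year mortality (assumed) | Reading of 1.9% | p(10) | Development events | Per candidate | Validation events | AUC interval width |
|---|---|---|---|---|---|---|
| 10% | crude | 3.67% | 772 | 48.3 | 525 | 0.051 |
| 20% | crude | 3.57% | 751 | 46.9 | 510 | 0.052 |
| 30% | crude | 3.46% | 728 | 45.5 | 495 | 0.052 |
| 40% | crude | 3.34% | 703 | 43.9 | 478 | 0.053 |
| 10% | Kaplan-Meier | 3.57% | 752 | 47.0 | 511 | 0.052 |
| 20% | Kaplan-Meier | 3.38% | 711 | 44.4 | 483 | 0.053 |
| 30% | Kaplan-Meier | 3.17% | 667 | 41.7 | 453 | 0.055 |
| 40% | Kaplan-Meier | 2.95% | 622 | 38.8 | 422 | 0.057 |

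At m = 30%, meeting both targets at 10 years would take about 23,100 + 15,700 = 38,800 per sex (crude) or 25,200 + 17,100 = 42,300 (Kaplan-Meier).

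**4. Counting events to 31 December 2016.** p(10.5) is about 4 to 5% above p(10). With no deaths it is 3.95%, giving 831 and 565 events. With deaths, both targets are met if 10-year mortality is below about 13% (crude) or 7% (Kaplan-Meier). At 30%, events are 757 and 514 (crude) or 694 and 472 (Kaplan-Meier).

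**5. Against the pools, at 10 years.** Assuming equal sexes, the 2:1 split gives N/3 development and N/6 validation subjects per sex.

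- 120,857: 40,286 and 20,143 subjects. Over the table's range of p(10), events are 1,477 to 1,189 and 739 to 595. Both targets hold.
- 90,000: 30,000 and 15,000 subjects. Events are 1,100 to 886 and 550 to 443. Development holds. Validation reaches 544 only at the top of the range (crude, 10% mortality).

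**The case against.** The constant rate is a declared planning assumption, and every printed figure follows from 3.8%. What the documents prove without an outside number is the 1% from compounding, and follow-up of 10.5 years more than repays that if nobody dies. Anything larger rests on a death rate the documents do not give and on the unstated type of the 1.9%. Relaxing only the mortality side is also one-sided. Entrants have no recorded complications and age by ten years, so the ESRD hazard may rise. At 20% or 30% mortality, a hazard in years 6 to 10 that is 14% or 22% higher cancels the loss on the crude reading (27% or 45% on the Kaplan-Meier reading). Finally, the sizes are minimums for an extraction of all eligible patients, and the larger pool clears both targets.

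Most of this stands as a limit on size. A reader might infer that the stated numbers cannot yield 800 and 544 events, or that any loss of person-time breaks both targets. The documents do not support that: with low mortality and events counted to the end of 2016, both targets are met. Nor do they support a claim that the study is too small.

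Three things do not fall away. At a constant rate the 10-year figure is below 3.8% whatever the mortality. The models are for 10-year risk, so the extra half-year may not count in a strict 10-year validation. And the adequacy claim is less secure on the 90,000 pool. Both pool figures come from data later than the 1 July 2006 index date, so neither is the eligible count. Appendix B might say more about the 1.9%, but the exact reproduction from 3.8% makes a hidden allowance for deaths unlikely.

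**Conclusion.** The point holds in direction and is modest and conditional in size. Under the plan's own constant-rate assumption, 21,053 and 14,307 subjects per sex are expected to give fewer than the implied 800 and stated 544 ESRD events by 10 years. The certain part is about 1%. For assumed 10-year mortality of 10% to 40%, the development shortfall is about 3% to 12% on the crude reading (772 to 703 against 800) and 6% to 22% on the Kaplan-Meier reading (752 to 622). In the plan's own terms that is 48 to 44, or 47 to 39, events per candidate instead of 50, and an AUC interval width of 0.051 to 0.053, or 0.052 to 0.057, instead of 0.050. These ranges rest on constant ESRD and death hazards and a 10-year horizon; longer counting or a rising ESRD hazard would narrow or close the gap. Whether it matters in practice depends on the eligible pool, and in the documents' figures mainly on validation with the smaller one.

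**What to change.** In the sample size section and Appendix B:

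1. State whether 1.9% is a crude proportion or a Kaplan-Meier estimate.
2. Take a death rate from the team's existing 5-year HA data and state it.
3. Recompute expected ESRD events as rate times person-time at risk, N x h/(h + d) x (1 - exp(-10(h + d))), with a sensitivity range for mortality and, if wanted, for a hazard that rises after year 5.
4. Either replace 3.8%, 21,053, 14,307, 544 and 35,360 with the recomputed figures, or keep the subject numbers and restate the events per candidate and AUC interval width they deliver. Say whether events after 10 years count.
5. Check the result against the expected eligible pool by sex after the 2:1 split, and reconcile 120,857 with 90,000.

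The cost is one recalculation from data already held and a few changed figures, which may look slightly less favourable. All eligible patients are extracted, so enrolment and data collection do not change.
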